5.6.2 Discontinuation of study treatment

Patients will be treated under hospital supervision during the treatment period. Discontinuation of study treatment for a patient occurs when study drug is stopped earlier than the protocol planned duration, and discontinuation can be initiated by either the patient or the investigator. For patients assigned to 1-day treatment arm, they will not be considered as treatment discontinuation if those discontinuation events occur after they have completed the treatment as assigned.

The investigator must discontinue study treatment for a given patient if, on balance, he/she believes that continuation would negatively impact the participation of the patient in the trial.

Study treatment must be discontinued under the following circumstances:

- Patient request
- Pregnancy (see [Section 6.5.6](#) and [Section 7.6](#))
- Use of prohibited treatment as per recommendations in [Section 5.5.8](#)
- Any situation in which study participation might result in a safety risk to the patient and/or any adverse events that in the judgment of the investigator, taking into account the patient's overall status, prevent the patient from continuing participation in the study
- Unsatisfactory therapeutic effect (see [Section 6.5.8](#))

- Emergence of the following adverse events: severe nausea/vomiting, severe pruritus, increases in QTcF to >500 ms (based on repeat Electrocardiograms (ECGs), development of ventricular arrhythmia or clinically significant (symptomatic) bradycardia (see [Appendix 3](#))
- Any laboratory abnormalities (e.g., LFT increase) that in the judgment of the investigator, taking into consideration the patient's overall status, prevent the patient from continuing taking the study medication (see [Appendix 2](#))
- Deviation from the planned dose regimen for the study drug

Patients who discontinue study drug for any of the above reasons may be given rescue medication at the discretion of the investigator and will be followed for the whole study duration until Study Day 29.

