9.1 Analysis sets

Randomized set

All patients who are randomized.

Full analysis set (FAS)

FAS will be comprised of all patients from Randomized set who take at least one dose of study treatment during the treatment period and whose baseline parasitaemia count is greater than 0. Following the intent-to-treat principle, patients will be analyzed according to the treatment group assigned to at randomization.

Safety set (SAF set)

Safety set includes all patients who take at least one dose of study drug during the treatment period. Patients will be analyzed according to treatment received. Full details will be described in the statistical analysis plan (SAP).

Per-protocol set (PPS)

PPS will be comprised of patients in FAS who

- did not have any important protocol deviations
- took at least 80% of assigned study medication(s). If a patient vomited the original dose but did not vomit the replacement dose, the patient is considered as taking the dose of study medication. Except for patients who are assigned to Coartem treatment, this requires that all patients take all KAE609 dosages as assigned

- did not take other antimalarial medications prior to Study Day 29 for reasons other than rescue medication given for *P. falciparum* related treatment failure, and
- met at least one of the following criteria: (a) classified as treatment failure before Study Day 8 (see [Section 6.5.8](#)), (b) absent from parasitaemia at Study Day 29, or (c) had valid PCR evaluations at baseline and at the time point with parasitaemia if parasitaemia is present at Study Day 8 or later.

Important protocol deviations for exclusion from PPS will be identified by the clinical team before the final database lock.

PK analysis set

All subjects in the safety analysis set who had evaluable PK parameter data and took at least 80% of assigned study medication.

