## 2.2 Analysis sets

**Randomized set (RAN)** : All patients who are randomized and not misrandomized if identified from IRT and who did not experience any important protocol deviation related to informed consent.

**Full analysis set (FAS)** : FAS will be comprised of all patients from Randomized set who take at least one dose of study treatment during the treatment period and whose baseline parasitaemia count is greater than 0. Following the intent-to-treat principle, patients will be analyzed according to the treatment group assigned to at randomization.

**Safety set (SAF set)** : Safety set includes all patients who take at least one dose of study drug during the treatment period. Patients will be analyzed according to treatment received.

**Per-protocol set (PPS)** : PPS will be comprised of patients in FAS who

- did not have any important protocol deviations
- took at least 80% of assigned study medication(s). If a patient vomited the original dose but did not vomit the replacement dose, the patient is considered as taking the dose of study medication. Except for patients who are assigned to Coartem treatment, this requires that all patients take all KAE609 dosages as assigned. For Coartem, the patient needs to take at least 5 doses of study drug to have taken 80%.
- did not take other antimalarial medications prior to Study Day 29 for reasons other than rescue medication given for *P. falciparum* related treatment failure, and
- met at least one of the following criteria: (a) classified as treatment failure before Study Day 8 (see [Section 2.1.1.1](#)), (b) absent from parasitaemia at Study Day 29, or (c) had valid PCR evaluations at baseline and at the time point with parasitaemia if parasitaemia is present at Study Day 8 or later.

Important protocol deviations for exclusion from PPS are specified in Table 5-9 and all other important protocol deviations will be identified by the clinical team before the final database lock.

**PK analysis set :** All subjects in the safety analysis set who had evaluable PK parameter data and with at least 80% compliance to study medication and who did not experience any important protocol deviation as mentioned in Table 5-9.

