## 2.4 Treatments (study treatment, rescue medication, concomitant therapies, compliance)

### 2.4.1 Study treatment / compliance

Number and percentage of doses taken will be presented by cohort and treatment group. The percentage will be calculated based on the planned number of doses per treatment group.

Planned number of doses in a treatment group = planned number of days of dosing x number of doses to be administered per day in that treatment group.

For example, planned number of doses is 1 for 'KAE609 10 mg and 6 for Coartem in cohort 1, etc.

Percentage of doses taken will be calculated as  $\frac{\text{actual number of doses administered}}{\text{Planned number of doses}} \times 100$

Compliance will be categorized by < 80 % and ≥80 % of doses taken and summarized by treatment group.

Number and percentage of patients with study drug vomiting and dose replacement will be presented by treatment group.

Average daily dosage and total dosage (in mg) of each study drug (KAE609, Coartem) will be summarized by cohort and treatment group.

$$\text{Average daily dosage} = \frac{\text{sum of actual doses taken in mg}}{\text{actual number of days of treatment}}$$

For Coartem, the tablets taken by patient are converted into mg based on the strength of tablet separately for the two active components of the drug, i.e., artemether and lumefantrine.

Note- If a patient vomited the original dose but did not vomit the replacement dose, the patient is considered as fully dosed. Doses that were vomited are excluded from the analyses although all patients who took at least one dose of study drug regardless of vomit or not are included in the Safety set.

Safety set will be used.

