## 2.9 Pharmacokinetic endpoints

PK concentrations below the limit of quantification will be treated as zero in summary statistics and for the calculation of pharmacokinetic parameters by non-compartmental method of analysis. Descriptive statistics of pharmacokinetic parameters will include arithmetic and geometric (means, standard deviation (SD), median, minimum and maximum, etc). Parameters such as AUCinf, AUClast, AUC0-t, Cmax, T1/2 and Tmax will be reported

[figure not shown]
[figure not shown]
using non-compartmental method of analysis (using Phoenix 6.4 or higher). 2-sided 90% confidence intervals for  $AUC_{0-24h}$ ,  $C_{max}$  and  $T_{max}$  PK parameters of KAE609 and Lumefantrine will be calculated by cohort and treatment group using normal or log-normal approximation as applicable.

[figure not shown]
All the PK data may be pooled for population pharmacokinetics analysis and the broad principles outlined in the Food and Drug Administration (FDA) Guidance for Industry: Population Pharmacokinetics would be followed.

[figure not shown]

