## 5.6 Rule of exclusion criteria of analysis sets

**Table 5-9 Protocol deviations and non-PD criteria leading to exclusion from analysis sets**

Analysis Set	PD (Description and ID) that causes Subjects to be excluded	Non-PD criteria that cause Subjects to be excluded
Randomized	
 
Informed Consent for study participation not obtained and subject entered trial (INCL06)
 
	
 
Not randomized
 
Misrandomized if identified from IRT
 

FAS	NA	
 
Not in Randomized set;
 
Baseline parasitaemia count is 0 or missing
 
No study drug taken
 

PPS	
 
Parasite specie is other than Plasmodium falciparum OR mixed infection (EXCL01)
 
Baseline plasmodium falciparum parasite count <500/uL or >50000/uL at screening visit (INCL03)
 
No fever within the past 24 hours at baseline (INCL04)
 
Received non-study concomitant antimalarial drugs between Day 1 and Day 29 without experiencing treatment failure (COMD02)
 
Patients who received concomitant prohibited medication which found to change the exposure that impacts efficacy. (COMD01b)
 
	
 
Not in FAS;
 
<80% of randomized study medication taken
 
Not classified as non-responder before Day 8, no positive blood smear parasite on Day 8 onwards, and blood smear parasite result is missing at Day 29.
 
Not classified as non-responder before Day 8, have at least one positive blood smear parasite result between Day 8 and Day 29 which cannot be determined as recrudescence or new infection based on PCR genotyping;
 

SAF	NA	
 
Not in Randomized set;
 
No study drug taken
 

PK	Patients who received concomitant prohibited medication which found to change the exposure that impacts interaction in PK parameters (COMD01c)	
 
Not in SAF
 
No evaluable pharmacokinetic parameter data
 
<80% of randomized study medication taken
 

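### The whole-regimen 80% rule for the PK set drops first-dose KAE609 profiles when a 3-day patient misses a later dose, for reasons that can depend on outcome

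*SAP*

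**What the plan says.** Three places define the PK set, and all three use the same threshold.

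- Protocol 9.1: "All subjects in the safety analysis set who had evaluable PK parameter data and took at least 80% of assigned study medication".
- SAP 2.2: patients from the safety set with evaluable PK parameters, "with at least 80% compliance to study medication and who did not experience any important protocol deviation". The sentence goes on to limit those deviations to the ones in Table 5-9.
- SAP Table 5-9, PK row: a patient is excluded with less than "80% of randomized study medication taken". The only deviation listed is COMD01c, a prohibited concomitant drug that affects PK.

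SAP 2.4.1 sets the denominator of compliance: "Planned number of doses in a treatment group = planned number of days of dosing x number of doses to be administered per day". SAP 2.2 applies the threshold itself, under the per-protocol set: "For Coartem, the patient needs to take at least 5 doses of study drug to have taken 80" per cent, while for KAE609 every assigned dose must be taken. None of these places makes an exception for first-dose parameters.

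SAP 2.9 plans two-sided 90% intervals for AUC0-24h, Cmax and Tmax; these "PK parameters of KAE609 and Lumefantrine will be calculated by cohort and treatment group". It names neither the analysis set nor the dosing day. SAP Table 5-6 has PK windows at 1, 2, 4, 6, 8, 12 and 24 h after the first dose, and again from 48 h onwards.

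**The concern.** The compliance rule is attached to the patient, while the parameters belong to a profile. A first-dose profile over 0 to 24 h is complete before dose 2 can influence it, and dose 3 cannot influence it at all. Removing it because a later dose was missed discards valid data.

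The discarding need not be random. The protocol gives several reasons to stop a 3-day regimen between doses:

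- Section 6.5.5 ends a 3-day regimen when a post-dose average QTc reaches 500 ms.
- Section 5.5.6 stops treatment and starts rescue on early treatment failure. Its criteria apply from 12 h, at 24 h and at 36 h, all ahead of a third daily dose at about 48 h.
- Section 5.6.2 lists severe nausea or vomiting, and "Any laboratory abnormalities (e.g., LFT increase) that in the judgment of the investigator" rule out further dosing. Appendix 2 adds specific liver stops.

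A single-dose patient with the same event has already taken the full regimen. Section 5.6.2 does not count that patient as a treatment discontinuation, and compliance stays at 100%. Among the KAE609 arms, the rule can therefore select on outcome in the 3-day arms only. PK is a stated secondary objective, so the exposure summaries for those arms could describe a selected group.

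**Working it through.** **1. Doses needed for 80%.** Compliance = doses taken / planned doses (SAP 2.4.1); the minimum is 0.8 × planned doses, rounded up.

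- Coartem, 6 planned: 0.8 × 6 = 4.8, so 5 doses. 5/6 = 83.3% passes; 4/6 = 66.7% fails. This reproduces the SAP's own figure of 5.
- KAE609 for 3 days, 3 planned: 0.8 × 3 = 2.4, so 3 doses. 2/3 = 66.7% and 1/3 = 33.3% both fail. This agrees with the SAP's statement that all KAE609 doses are needed.
- KAE609 single dose: 1/1 = 100%.

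**2. Patients under the rule.** The arm sizes (Protocol 3.1) and allocation ratios (Protocol 5.2) give cohorts of 20 + 30 + 50 + 50 + 30 + 30 = 210, the planned total. The 3-day KAE609 arms are 10 mg (10), 25 mg (20) and 50 mg (20): 50 of 150 KAE609 patients, in 3 of 9 KAE609 arms.

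**3. Chance of losing anyone.** The documents give no rate of stopping before dose 3, so q is an assumption. Expected loss = n × q; P(at least one lost) = 1 − (1 − q)^n.

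| q (assumed) | n = 10: expected; P(≥1) | n = 20: expected; P(≥1) |
|---|---|---|
| 5% | 0.5; 40% | 1.0; 64% |
| 10% | 1.0; 65% | 2.0; 88% |
| 25% | 2.5; 94% | 5.0; over 99% |

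The only related figures are the early-failure rates of an earlier study in Protocol 3.6: none at 15 mg and 30 mg, 25% at 20 mg (one patient) and 42% at 10 mg (three patients). They are a loose guide, because they come from small groups and SAP Section 3 lists the 10 to 30 mg study separately from the 3-day one. They also overstate stops before dose 3: the 48 h criterion coincides with dose 3 and the 72 h criterion follows it.

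**4. Precision.** At a fixed SD, width is proportional to 1/√n.

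- Losing 1 of 10: √(10/9) = 1.054, about 5% wider. With 90% t-quantiles (1.860/1.833), 1.054 × 1.014 = 1.07.
- Losing 4 of 10: √(10/6) = 1.291, about 29% wider. With t-quantiles (2.015/1.833), 1.291 × 1.099 = 1.42.

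**5. Selection, as an upper bound.** Assume log-normal exposure with CV 40%, so σ = √ln(1.16) = 0.385, and stops confined to one extreme tail of exposure. The geometric mean is then multiplied or divided by exp[σ·φ(z_q)/(1 − q)]: 1.043 at q = 5%, 1.078 at 10% and 1.177 at 25%. It rises if low-exposure failures are dropped and falls if high-exposure toxicity stops are dropped. If stopping is unrelated to exposure there is no bias, only a smaller n.

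**The case against.** Much can be said for leaving the rule alone, and part of it stands.

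- **The data are not destroyed.** SAP Table 2-5 lists concentrations and PK parameters, and SAP 2.9 allows a population PK analysis of all PK data. This stands, though that analysis is optional and neither route supplies the planned group intervals.
- **The dosing day is not stated.** If AUC0-24h and Cmax were meant for Day 3, requiring every dose would be right. First-dose sampling in the 3-day arms is inferred from Table 5-6, which maps windows and is not split by drug; the assessment schedule is not readable here. Its 24 h window also runs to 38 h, past dose 2. This stands as a limit, and shows that the missing specification itself needs repair.
- **Liver cases.** A reader might infer that the rule removes the hepatic cases the trial is about. The documents do not support that. Enzyme rises are expected to peak within 14 days (Protocol 3.1), and Appendix 2 keeps patients between 5 and 8 × ULN on drug unless the elevation lasts beyond two weeks. Most such patients should complete three doses and stay in.
- **Exposure thresholds.** A reader might also link this to the 110 mg rationale in Protocol 3.6. That passage is conditional and concerns the single-dose Cohorts 5 and 6, where this mechanism does not operate. The text of the SAP section on PK/PD analyses is not available, so nothing can be said about the set it uses.
- **Single versus repeated dosing.** Equal doses given once and for 3 days sit in different cohorts, and no comparison of their first-day exposure is planned.
- **Scope.** Coartem patients with 4 of 6 doses are excluded too, but that arm tolerates one missed dose; 3-day KAE609 tolerates none.

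**Conclusion.** The point holds in a limited form. The 80% rule, the dose count and the stopping rules are all explicit. Together they remove a 3-day KAE609 patient's first-dose profile from the PK-set summaries after a single later missed dose. Fifty planned patients are subject to this, and the likelier routes to exclusion are QTc and early failure.

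The effect is a loss of n and possible selection on exposure in the 3-day arms. The documents fix neither its size nor its direction; the interval widening and shifts in the working rest on assumed stopping rates and, for the shifts, an assumed CV. The conclusion also assumes that the summaries in SAP 2.9 use the PK set and include first-dose parameters, which is implied but not written. The primary hepatic analysis and the sample-size figures are unaffected. The change is still worth making, because the rule discards valid data for reasons that can be outcome-related and the repair is cheap.

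**What to change.** - In SAP 2.2 and Table 5-9, define PK evaluability per profile.
- Include Day-1 KAE609 parameters (AUC0-24h, Cmax, Tmax) for every Safety-set patient who retained dose 1, has an evaluable 0–24 h profile and has no COMD01c deviation affecting that profile. Say that the 24 h sample must precede any second dose, and how a profile is classed if rescue starts before 24 h.
- Apply the all-doses requirement (KAE609) or 5-of-6 requirement (lumefantrine) only to Day-3 and whole-regimen parameters.
- In SAP 2.9, state the analysis set and the dosing day for AUC0-24h, Cmax and Tmax.
- Align Protocol 9.1, or record the difference in SAP Section 4, which at present reports no changes from the protocol.

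The cost is SAP wording and one evaluability flag per profile, with no new samples. The downside is that n may differ between Day-1 and Day-3 rows, so each row should show its own n. If the change comes after database lock, label the per-profile summary as supplementary; the SAP history already records one update after lock.

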### **2.2.1 Subgroup of interest**

The following subgroups will be used for descriptive summary or figures of the selected efficacy and safety analyses. The details will be provided in the corresponding sections.

- Sex (male vs female)
- Patients with baseline parasitaemia  $\geq 10000/\mu\text{L}$

## **2.3 Patient disposition, demographics and other baseline characteristics**

### **2.3.1 Medical history**

Any condition entered on the *Relevant medical history / current medical conditions* CRF will be coded using the MedDRA dictionary. They will be summarized by primary system organ class (SOC) and preferred term (PT) of the MedDRA dictionary. A separate summary will also be provided on medical conditions that were active at the time of screening.

Medical conditions that are present after informed consent has been signed but before the first dose of study medication is administered are collected in the adverse event panel and will be summarized separately from adverse events.

The Medical History conditions captured on the eCRF “Protocol solicited events ” will be tabulated separately.

History of use of alcohol will also be summarized.

Unless otherwise specified, analyses will be based on the randomized set.

### **2.3.2 Patient demographics and other baseline characteristics**

Demographic data and baseline disease characteristics will be presented descriptively and tabulated (n, mean, standard deviation, median, minimum, and maximum for continuous variables; n and percent for categorical variables) by cohort and treatment group, as well as overall, using Randomized set. If many patients (Overall > 5%) are excluded from FAS, summary will also be provided for the FAS.

Following demographic variables will be summarized

- Age and age categories ( <65 vs  $\geq 65$  yrs)
- Sex (male, female)
- Subject child bearing status (able to bear children, premenarche, post menopausal, sterile of child bearing age)
- Race
- Ethnicity

- Body height (cm)
- BMI and BMI categories (<16, 16 to 25, >25) (kg/m^2)

Following disease characteristics at baseline will be summarized

- Body temperature and the number and percentage of patients for categories (<37.5, 37.5 to <39, ≥39) (°C) for (*axillary*) and < 38.0°C, 38.0 to <39.8, ≥ 39.8 for other routes)
- Presence of Falciparum species: (P. Falciparum asexual forms, P. Vivax, P. Ovale, P. malariae, P. Knowlesi, n (%))
- P. falciparum asexual forms density per micro ltr. and the number and percentage of patients for categories (<500, 500 to <2,000, 2,000 to <5,000, 5,000 to <15,000, 15,000 to <50,000, ≥50,000 parasites /μL)

### 2.3.3 Patient disposition

The number and percentage of patients screened will be presented for overall. In addition, the reasons for screen failures will be provided. The number and percentage of patients who completed each epoch (treatment and follow-up) and who discontinued each epoch prematurely (including the reason for discontinuation) will be presented by cohort for each treatment group and overall.

For each protocol deviation, the number and percentage of patients for whom the deviation applies will be tabulated.

Randomized set will be used.

## 2.4 Treatments (study treatment, rescue medication, concomitant therapies, compliance)

### 2.4.1 Study treatment / compliance

Number and percentage of doses taken will be presented by cohort and treatment group. The percentage will be calculated based on the planned number of doses per treatment group.

Planned number of doses in a treatment group = planned number of days of dosing x number of doses to be administered per day in that treatment group.

For example, planned number of doses is 1 for 'KAE609 10 mg and 6 for Coartem in cohort 1, etc.

Percentage of doses taken will be calculated as  $\frac{\text{actual number of doses administered}}{\text{Planned number of doses}} \times 100$

Compliance will be categorized by < 80 % and ≥80 % of doses taken and summarized by treatment group.

Number and percentage of patients with study drug vomiting and dose replacement will be presented by treatment group.

Average daily dosage and total dosage (in mg) of each study drug (KAE609, Coartem) will be summarized by cohort and treatment group.

$$\text{Average daily dosage} = \frac{\text{sum of actual doses taken in mg}}{\text{actual number of days of treatment}}$$

For Coartem, the tablets taken by patient are converted into mg based on the strength of tablet separately for the two active components of the drug, i.e., artemether and lumefantrine.

Note- If a patient vomited the original dose but did not vomit the replacement dose, the patient is considered as fully dosed. Doses that were vomited are excluded from the analyses although all patients who took at least one dose of study drug regardless of vomit or not are included in the Safety set.

Safety set will be used.

